16.6 Follow-up

Following the completion of the study, each participant will be given a contact number at Massey University, where they can contact a member of the experimental team should any adverse effects develop.

17 DATA MANAGEMENT

17.1 Electronic data storage

Data collected are listed in sections 16.2 to 16.5.

The researchers will capture all data required in the Protocol into a secure web-based password-protected repository only accessible by the researchers. Hard copies of laboratory data sheets and mass spec output feed will be scanned and saved, and the hard copies will be saved in swipe-card access or locked office areas.

17.1.2 Access rights

Designated researchers will be provided with a username and password to access the study database. This username/password pair may be used by a single individual only; passwords must not be shared with anyone else.

17.2 Audit trail

The clinical data management systems developed for this study comply with Good Clinical Practice (GCP) predicate rule requirements, laws, and regulations (Personal data protection) and allows an audit of actions performed by users.

18 AUDIT OF ACTIONS PERFORMED BY USERS STATISTICS

18.1 Effects to be estimated.

Protein net balance parameters, amino acid concentration AUC, sensory Likert scales.

18.2 Sample size calculations

The sample size was determined from the only relevant available NB data of Kim et al., 2018 where the egg vs. cereal difference (expected effect size between no and excellent quality) was 7 g net protein accretion in 165 min of infusion time, and the standard error derived from the p-value of 1.53 g (Kim et al., 2018). With the smallest important change of 2.2 g protein, using traditional null hypothesis significance testing with 5% type-1 and 20% type-2 error rates, a sample size of 8 was required (Hopkins, 2006), which we felt provided sufficient precision for the 30% of the anticipated difference between high and excellent protein quality, relative to the no quality contrast.

18.3 Randomization

Treatment sequences will be randomly assigned to participants in the Youden square sequence for n=3 treatments.

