11 STUDY DESIGN

11.1 Type of Study

A randomized controlled trial with a crossover design (cRCT) comprising three arms in a clinical laboratory setting.

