12.5 Subject withdrawal criteria

The study participants are entitled to withdraw from the study at any time voluntarily and for any other reason without affecting their access to the treatment or their future treatment by the Investigator. In addition, a participant may be withdrawn from the study at any time for reasons including, but not limited to, the following:

- Investigator's medical decision when continuing the study would compromise the safety of the participant.
- The participant is unwilling or unable to adhere to protocol requirements.
- In the event of injury.
- Non-compliance with the dietary intervention protocols (pre-intervention control diet and interventional diet).
- Observation of adverse effects.
- Absence from more than two testing sessions.

Participants will be notified by the Investigator prior to withdrawal from the study/investigational product in writing with a full explanation for their withdrawal. Depending on the time of withdrawal from the study protocol, participants will be followed up as follows:

- Prior to or following participation in any trials, participants will be provided standard notification of reasons for withdrawal.
-

- During the trials, participants will be withdrawn following non-compliance to the interventional diets, inability to maintain a normal diet and allowed physical activity patterns, or any observed adverse effect. Participants' condition will be monitored for 24 hours following withdrawal if due to adverse effects.

Participants withdrawn during the study will be replaced in randomized sequence order until n=8 is complete or a maximum dropout replacement of 2 is met or exceeded.

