13.1.4 Randomization technique and coding

The participants and investigators will be aware of the treatment assignments. Three abbreviation codes will be applied. The codes will be (CP1) Quinoa, Quorn, chickpeas, and bread, (CP2) Chickpeas, quinoa, tofu, and bread, and (CP3) Chickpeas, quinoa, and bread. The abbreviations are CP1, CP2, and CP3. Participants will be allocated to sequences based on the Youden square design. The randomization list with participant number and the code sequence will be shared with the study investigators to select the abbreviation label for each participant on each intervention day.

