16 CONDUCT OF THE STUDY

16.1 Subject recruitment

A total of 8 men and women (67-77 years of age) will be required to complete the study, with contingency for another 2 if required due to dropout. The target is 4 in each gender, with contingency to complete 5 and 3 of either gender combination, depending on recruitment. Participants will be recruited from the local Auckland community via general advertisement at the University, University participant databases, social media, community notice boards, web pages, and word of mouth. Each participant will have the study outline and requirements explained in detail. At this point, they will be allowed to ask questions regarding the study and answer a health questionnaire. An inclusion checklist will be completed after the subject has agreed to participate by signing the consent. Subjects will be enrolled after fulfilling all inclusion criteria and presenting none of the exclusion criteria.

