16.4 Visits 2-3 (days approx. 8 to 15)

- A repeat of Visit 1 but with another randomized order of treatment, allowing for a minimum period of 7 days of washout between visits to minimize any carry-over effects.

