18.6 Statistical analysis

18.6.1 Primary analysis

Outcomes will be analysed using a mixed model analysis of variance. Fixed effects will be meal condition and time (where relevant). The random effect will be subject to an unstructured covariance matrix to account for correlated data within the crossover. Data will be log-transformed to improve linearity and model fit and to express outcomes as percent differences. Primary outcomes (PS, PD, and NB) will be referenced to our estimate of the smallest important clinical changes. Data will be presented as the least-squares mean and uncertainty (95% confidence interval) and, where useful, the effect size as a standardized mean difference.

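### The primary crossover model has no visit (period) term, so any visit-to-visit change widens the meal comparisons

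*Protocol*

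**What the plan says.** - **Design.** Protocol 11.1 describes "A randomized controlled trial with a crossover design (cRCT) comprising three arms in a clinical laboratory setting". Section 8 places the three test visits on days 1, 8 and 15.
- **Allocation.** Section 13.1.4: "Participants will be allocated to sequences based on the Youden square design". Section 18.3: "Treatment sequences will be randomly assigned to participants in the Youden square sequence for n=3 treatments". Neither gives the number of sequences or of replicate squares.
- **Numbers.** Section 16.1: "A total of 8 men and women (67-77 years of age) will be required to complete the study, with contingency for another 2". Section 12.5: "Participants withdrawn during the study will be replaced in randomized sequence order until n=8 is complete or a maximum dropout replacement of 2".
- **Model.** Section 18.6.1: "Fixed effects will be meal condition and time (where relevant", closing the bracket there, and then "The random effect will be subject to an unstructured covariance matrix to account for correlated data within the crossover". The Synopsis (section 7) gives the same two fixed effects. Section 18.6.2 carries the model over to the secondary outcomes, leaving only the sensory scales untransformed.
- **Protection against visit effects.** Section 16.4 repeats the visit in another order, "allowing for a minimum period of 7 days of washout between visits to minimize any carry-over effects".

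**The concern.** A Youden or Latin square arranges treatments against visits so that differences between visits can be separated from differences between treatments. That benefit is fully realised only if visit is in the model. The protocol lists its fixed effects twice and visit is in neither list, so this is a stated model and not a detail left open.

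The word time does not clearly fill the gap. The Synopsis reduces the four-hour response to an AUC divided by time, which gives one value per person per visit. The qualifier about relevance fits sampling time, which exists for repeated samples and the sensory scales but not for such summaries.

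If visit is left out, any systematic change from visit 1 to visit 3 is counted as unexplained within-person variation. Because eight people cannot balance the square, a small part also enters the meal differences. With 8 × 3 = 24 planned observations there is little precision to spare.

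**Working it through.** **Inputs.** Three meals, three visits and 8 completers (11.1, 16.1). From 18.2: smallest important change 2.2 g, error figure 1.53 g, 5% and 20% error rates. Drift size: not in the protocol, so assumed linear at d = 0, 0.5, 1 or 2 g per visit.

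**1. The plan's own sample size.** n = 2 × [(1.960 + 0.842) × 1.53 / 2.2]² = 7.59, rounded up to 8. This reproduces the stated 8 when 1.53 g is used as a within-person SD, although 18.2 calls it a standard error. I use 1.53 g as the within-person SD below, as an assumption.

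**2. Balance.** With as many visits as meals, a Youden layout is a 3 × 3 Latin square. Take sequences ABC, BCA and CAB with 3, 3 and 2 people. Counts at visits 1, 2 and 3 are:

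| Meal | Visit 1 | Visit 2 | Visit 3 | Mean position |
|---|---|---|---|---|
| A | 3 | 2 | 3 | 2.000 |
| B | 3 | 3 | 2 | 1.875 |
| C | 2 | 3 | 3 | 2.125 |

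**3. Bias without a period term.** Each contrast is shifted by d times the difference in mean position: 0.125d, 0.125d and 0.25d in absolute value. At d = 1 g the largest shift is 0.25 g, or 0.25 / 2.2 = 11% of the smallest important change.

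**4. Residual error without a period term.** Code the visits −d, 0, +d. Each person contributes 2d² within person, so eight contribute 16d². Meal absorbs 8 × (0.125² + 0.125²) d² = 0.25d². The remaining 15.75d² is spread over 24 − 8 − 2 = 14 df, which adds 15.75 / 14 = 1.125d² to the residual variance:

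residual SD = √(1.53² + 1.125d²)

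This gives 1.53, 1.62, 1.86 and 2.62 g for d = 0, 0.5, 1 and 2.

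**5. Half-widths.** Without period: t(14 df) × √0.25 = 2.145 × 0.5 = 1.072 residual SDs. With period: 12 df and variance factor 0.2540, so 2.179 × 0.504 = 1.098 SDs, or 1.68 g at any drift. Averages over 20,000 simulated trials are slightly lower, because the mean of an estimated SD lies below its root mean square.

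| d (g per visit) | No period, formula | No period, simulated mean | With period, simulated mean |
|---|---|---|---|
| 0 | 1.64 | 1.61 | about 1.65 |
| 0.5 | 1.74 | 1.71 | about 1.65 |
| 1 | 2.00 | 1.96 | about 1.65 |
| 2 | 2.80 | 2.78 | about 1.65 |

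**6. Error rates.** At d = 1 g without period, the type I error falls to about 0.02. Power for 2.2 g falls from about 0.76 to between 0.49 and 0.72, depending on the contrast and its direction. With period fitted, power stays at about 0.74 to 0.75 and type I error at about 0.05.

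**7. Other reading of the covariance.** If unstructured means a separate variance for each meal and covariance for each pair, each contrast behaves like a paired difference with about 7 df. For A minus B the position differences are −1 (five people) and +2 (three people). Their variance is (17 − 8 × 0.125²) / 7 = 2.41, so drift adds 2.41d² to 2 × 1.53² = 4.68. At d = 1 the SD of the difference goes from 2.16 to 2.66 g, up 23%. The direction and rough size are the same; the half-widths in step 5 would not carry over.

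**The case against.** **Visit effects may be small.** Each intervention is a single meal, visits are at least a week apart, a controlled dinner and an overnight fast precede each one, and arrival time is held constant. One person's visits are planned about a week apart, so change over the testing season falls mainly between people and is absorbed by the subject effect. Samples are assayed in batches, and nothing shows that runs follow visit order. This stands: the protocol gives no ground for a large drift, and at 0.5 g per visit the loss is under 4% (1.71 against 1.65 g). The washout, however, addresses carry-over and not a general change from visit to visit.

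**Time might mean visit.** If so, the gap closes, but the text would have to say it.

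**The illustration is not the stated model.** The plan log-transforms the data, while the figures here are in grams. They show direction and order of size only.

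**Stronger readings that the document does not support.** A reader might infer that the omission biases the trial or produces false positives. It does not: the bias is at most 0.25d under 3/3/2, it averages to zero if the short sequence is chosen at random, and tests become conservative. A reader might also infer that a single cyclic square ties each meal to one predecessor and so confounds carry-over. The protocol does not state how many squares are used, and no carry-over size can be set against the seven-day washout. Finally, a reader might conclude that the sequences must be redrawn from all six orders. Eight people cannot fill six orders either. Over the 15 ways of repeating two different orders, the largest imbalance is 0 in three, 0.25d in six and 0.375d in six.

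**Conclusion.** The point holds for the model in 18.6.1 and the Synopsis: a three-visit crossover allocated by a square is analysed without the visit term. The consequence is lost precision whenever there is a visit effect. At an assumed 1 g per visit, intervals are about 19% wider than with the term (1.96 against 1.65 g); at 2 g per visit they are about two thirds wider. Shift in the contrasts is a minor second effect.

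These sizes rest on an assumed linear drift, 1.53 g taken as the within-person SD, a gram scale, a random-subject model and a 3/3/2 fill. The unevenness of eight people is not itself the fault: once visit is fitted, it raises the variance factor only from 0.2500 to 0.2540.

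**What to change.** In 18.6.1 and the Synopsis, add visit (period) as a categorical fixed effect with three levels, for all primary and secondary outcomes. Name it separately from sampling time, and state which outcomes use sampling time.

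If there is no drift, the cost is 2 residual df (14 to 12) and about 2.4% in width (1.098 / 1.072). No extra data or participants are needed.

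Stating the number of sequences would help the reader. Using all six orders is optional and does not replace the period term.

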18.4 Interim Analysis

Not applicable

18.5 Datasets to be analysed

18.5.1 *Full analysis dataset*

All participants provided at least 2 complete treatments.

18.5.2 *PP analysis dataset*

All participants providing a full set of 3 treatments finished.

18.5.3 Missing values and outliers

No imputations are foreseen. The mixed model will consider incomplete sequences as missing at random.

18.6 Statistical analysis

18.6.1 Primary analysis

Outcomes will be analysed using a mixed model analysis of variance. Fixed effects will be meal condition and time (where relevant). The random effect will be subject to an unstructured covariance matrix to account for correlated data within the crossover. Data will be log-transformed to improve linearity and model fit and to express outcomes as percent differences. Primary outcomes (PS, PD, and NB) will be referenced to our estimate of the smallest important clinical changes. Data will be presented as the least-squares mean and uncertainty (95% confidence interval) and, where useful, the effect size as a standardized mean difference.

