Participants will remain rested during sampling and may do computer work, watch TV, or relax. There will be a minimum 1-week washout between trials. The 4-hour post-prandial response will be calculated as the area under the curve (AUC) using the post-absorptive concentration as the baseline reference. The AUC will then be divided by time to determine the average increase in post-prandial plasma concentration. We will calculate the whole-body PS, PB, and NB (NB = PS - PB) using the standard steady-state isotope dilution equations (Jonker et al., 2019). Outcomes will be analysed using mixed model analysis of variance (SAS, Cary, NC). Fixed effects will be meal condition and time (where relevant). Random effects will be subject to an unstructured covariance matrix to account for correlated data within the crossover. Data will be log-transform to improve linearity and model fit and to express outcomes as percent differences. Primary outcomes (PS, PB, and NB) will be referenced to our estimate of the smallest important clinical changes. Data will be presented as the least-squares mean and uncertainty (confidence interval) and, where useful, the effect size as a standardized mean difference with modified Cohen d effect size descriptors for the mean and breadth of the confidence interval. Results will be used to determine the influence of protein quality in a whole-food matrix defined by DIAAS and the effect of combining proteins to modify DIAAS on the primary health outcome of whole-body protein net balance governing lean mass homeostasis in older adults.

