10.3 Secondary objectives

To validate DIAAS as a metric of bioavailability of key and limiting amino acids in the plasma following meal ingestion from analysis of total plasma IAA, leucine, and lysine concentrations and total 4-h post-prandial AUC. To study the glycemic response to meals as a measure of health index and the insulin response as part of the mechanisms driving PS.

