10.4 Secondary outcomes

Post-prandial plasma:

1. AUC for total IAA concentration
2. AUC leucine (anabolic trigger for protein synthesis)
3. AUC lysine (first limiting amino acid)
4. Insulin
5. Glucose

Sensory analysis in response to the meals using linear Likert scales postprandial. This will be measured at 0 minutes preprandial and 30, 90, and 240 minutes postprandial.

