16.5 Biological samples

Arterialized venous blood will be collected from a dorsal hand vein heated hand method in a Perspex chamber (~55°C air temperature) (Gallen and Macdonald 1990). Blood samples will be collected from a superficial dorsal vein of the hand and placed in a thermostatically controlled box to mimic arterial samples (time points for blood sample collection can be viewed in Figure 1). Triplicate arterialized-venous blood samples will be collected at -20, -10 and 0 minutes after the infusion begins to measure pre-prandial enrichment of amino acids and glucose and insulin plasma concentrations. Post-prandial measurements will be collected between time 0-240 minutes. Each intervention will involve a protein meal given 90 minutes after the start of the infusion, and approximately 140 mL of blood will be collected per intervention. An overview of the infusion protocol is provided below (Figure 1).

[figure not shown]

Figure 1. Overview of the study protocol. In randomized order, participants receive one of the five meals at time=0 (x). A primed continuous infusion of Phe and Tyr stable isotopic tracers is used to calculate whole-body protein synthesis, breakdown, and net balance of the 4-h post-prandial period.

Blood samples will be collected and placed in heparinized tubes to prevent clotting. To minimize potential reactions, the samples will be immediately placed on ice, followed by deproteinization of the blood plasma with Trichloroacetic (TCA) (Appendix 2), the remaining untreated blood plasma will also be collected. The deproteinized and untreated plasma will be frozen and stored at -80°C until further analysis. To analyse the samples, we will use a liquid chromatography-electrospray ionization-tandem mass spectrometry quadrupole-time of flight (LC/MS-QTOF) system to determine isotope tracer enrichments, concentrations, and insulin. The amino acid enrichment will be expressed as a tracer:tracee ratio corrected for natural background abundance. An automatic analyser will determine plasma glucose concentrations. We analyse the samples in batches to minimize potential variability, and all procedures follow established protocols and guidelines. Quality control measures will be taken throughout the analysis to ensure the accuracy and precision of the results. Additionally, some blood samples might be analysed overseas.

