18.6.2 Secondary analyses

The statistical analysis on secondary outcomes will be as for the primary, except sensory scale data will not be log-transformed.

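### The meal-plus-time model for secondary time courses averages the pre-meal sensory score into the meal effect and cannot show when meals differ; whether glucose and insulin are affected is left open

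*Protocol*

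**What the plan says.** The primary analysis (18.6.1, and likewise the synopsis) is a mixed model for which the protocol says "Fixed effects will be meal condition and time (where relevant"). It names no meal-by-time term and no baseline covariate. Section 18.6.2 extends this: "The statistical analysis on secondary outcomes will be as for the primary, except sensory scale data will not be log-transformed".

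The secondary outcomes come in different forms.

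- **Sensory scales.** Section 10.4 says "This will be measured at 0 minutes preprandial and 30, 90, and 240 minutes postprandial". No AUC or change score is defined for them, so time is relevant and the pre-meal score is one of four outcome times.
- **Amino acids.** Total IAA, leucine and lysine are each listed as an AUC.
- **Glucose and insulin.** They are listed without the AUC label, but under the heading "Post-prandial plasma". Section 10.3 gives the aim as "To study the glycemic response to meals as a measure of health index and the insulin response". Section 16.5 takes samples at -20, -10 and 0 min "to measure pre-prandial enrichment of amino acids and glucose and insulin plasma concentrations", and then says "Post-prandial measurements will be collected between time 0-240 minutes".
- **General summary of the response.** The synopsis says "The 4-hour post-prandial response will be calculated as the area under the curve (AUC) using the post-absorptive concentration as the baseline reference", then divides by time. It does not say which analytes this covers. Section 18.1 mentions AUC only for amino acids and does not list glucose or insulin.

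**The concern.** A model with only main effects of meal and time imposes one meal difference at every sampling time, including any time before the meal. Its meal test asks whether the meals have equal averages over all fitted rows. The question of interest is the response to the meal: how far, and when, values differ after eating.

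Two separate losses follow. First, a pre-meal row carries no effect of eating the meal, so it pulls the estimated meal difference towards zero. Second, differences that appear early and fade, or curves that cross, are partly or wholly averaged away, and the model offers no contrast at a given time that could reveal them. With 8 participants, a null result produced in this way could easily be read as evidence that the meals do not differ.

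**Working it through.** **Plan's own figure.** The protocol gives no effect size, variance or power for the sensory scales, glucose or insulin. Its sample size of 8 concerns net protein balance and plays no part here.

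**Dilution, sensory scales.** Inputs from 10.4: b = 1 pre-meal time and k = 3 post-meal times. Let the difference between two meals be 0 before the meal and δ at each post-meal time. With complete data and equally weighted rows, the meal contrast in a meal + time model is the average difference over rows:

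(b × 0 + k × δ) / (b + k) = 3δ/4 = 0.75δ.

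The same model returns this one value at 30, 90 and 240 min.

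**Dilution, glucose and insulin, only if pre-meal rows are fitted.** b = 3 (16.5). The number of post-meal samples is not in the text, so k is assumed to be 5 to 12. The factor k/(k + 3) is 5/8 = 0.63, 6/9 = 0.67, 8/11 = 0.73, 10/13 = 0.77 and 12/15 = 0.80. If the outcome is a baseline-referenced AUC, there is one value per visit, no time factor and no dilution.

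**Loss of power.** Simulation of 20,000 trials per case: 8 participants, 3 meals, times 0/30/90/240 min, residual SD 1, participant-by-visit SD 0.5, alpha 5%, middle meal halfway between the extremes. Effects are differences between the extreme meals in residual SD units. All of these are assumptions. The additive meal test uses the mean of all four rows (2, 14 df). The meal-by-time test uses the three post-meal rows (4, 42 df).

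| Case | Additive meal test, 4 rows | Meal-by-time, 3 post-meal rows |
|---|---|---|
| 2.25 at 30 min only | 23% | 81% |
| Crossing: +1.8 at 30, -1.8 at 240 | 5% | 98% |
| Fading: 2.25, 1.125, 0 | 47% | 67% |
| Constant 1.5 after the meal | 72% | 5% |

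In the constant case, the post-meal average contrast without the pre-meal row has 89% power. Each test rejects about 5% of the time when there is no effect. With visit SD 1 the additive test falls to 12% in the first case and 21% in the fading case, and stays at 5% for crossing curves.

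A second set of assumptions (visit SD 0.3, smaller effects) gives the same pattern for the additive test against the post-meal average:

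- constant shift of 1.0: 53% against 69%
- difference of 1.5 at 30 min only: 17% against 22%
- crossing at ±1.5: 5% against 5%

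The post-meal average therefore removes the dilution but does not detect shape. That needs the meal-by-time term.

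**Using both tests.** If a difference were declared when either the post-meal average test or the meal-by-time test rejects, the false-positive rate would be about 1 - 0.95² = 9.75%. The simulated value is 9.6%.

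**The case against.** Several points can be made for the plan.

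*The list of fixed effects may not be exhaustive.* Naming meal and time does not literally exclude their interaction, and a statistical analysis plan not at hand could add it. This stands as a caution. But the protocol does state a model and then extends it to the secondary outcomes with a single exception, so as written the interaction is not part of it.

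*Glucose and insulin.* A reader might infer from the missing AUC label and the pre-meal sampling that pre-meal glucose and insulin values enter as response rows. The documents do not support that. Taking a sample is not the same as fitting it, the two outcomes stand under a post-prandial heading, and the synopsis describes a baseline-referenced AUC that may cover them. Equally, nothing says that they are AUCs. The form of the outcome is unsettled, and this objection stands.

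*The primary analysis.* The sentence sits in the primary analysis section, so a reader might infer that the primary conclusion is at risk. It is not: the synopsis and 10.4 support reading PS, PB, NB and the amino acid AUCs as one summary per meal.

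*The pre-meal sensory score might differ by meal.* Participants know their assignment (13.1.4) and the scale items are not given, so expectation could affect the score at time 0. The 3/4 factor assumes that it does not. If it does, averaging that score into the meal effect is still not a measure of response.

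*The interaction test is no cure-all.* This is correct. On post-meal rows it has about 5% power for a constant shift, so it should not replace the average contrast.

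**Conclusion.** The point holds firmly for the sensory scales and conditionally for glucose and insulin. It concerns secondary outcomes only.

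For the sensory scales, the model as written dilutes a constant post-meal difference to 3/4, gives no time-specific contrast, and has no more than alpha-level power for curves that cross and average to zero. The 3/4 follows from the protocol's sampling times, given complete data, equally weighted rows and no meal difference at time 0. The power figures rest wholly on assumed effect sizes, shapes and variances. They show the direction and possible extent of the loss and do not predict it for this trial.

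For glucose and insulin, the loss of shape information arises if they are fitted as time courses. Dilution (factor 0.63 to 0.80 for an assumed 5 to 12 post-meal samples) arises only if the pre-meal values are also response rows. Neither is stated. The change is worth making, because a null secondary result could otherwise be a product of the model.

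**What to change.** In 10.4 and 18.6.2, state whether glucose and insulin are analysed as the baseline-referenced AUC of the synopsis (one value per visit, no time factor) or as time courses.

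For the sensory scales, and for any other outcome kept as a time course, specify:

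- fixed effects of meal, time and meal-by-time, fitted to the post-meal samples only;
- the pre-meal value as a covariate, not as a response row;
- a participant-by-visit random effect, so that samples from one visit are not treated as independent;
- the post-meal average meal contrast as the single main test, with the meal-by-time test and time-specific contrasts as supportive.

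The cost is wording and a few more parameters in a trial of 8 participants; no new data are needed. Designating one main test is essential, because accepting either test would raise the false-positive rate to about 10%. The price of that choice is that crossing curves will show only in the supportive analyses.

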6 ABBREVIATIONS - DEFINITIONS

AE	Adverse Event
AUC	Area Under the Curve
CRA	Clinical Research Associate (synonym: monitor)
CRF	Case Report Form
CPM	Clinical Project Manager
DIAAS	Digestible Indispensable Amino Acids Score
GCP	Good Clinical Practice
IAA	Indispensable Amino Acids
IEC	Independent Ethics Committee
IRB	Institutional Review Board
ITT	Intent-To-Treat
MP	Method and Procedure: providing all the information necessary to carry out activities efficiently, safely, and in an authorized manner.
NB	Net Protein Balance (protein synthesis minus protein degradation)
PD	Protein Degradation (i.e., protein breakdown)
PP	Per-Protocol
PS	Protein Synthesis
SAE	Serious Adverse Event
SOP	Standard Operating Procedure: (Providing all the information necessary to use equipment efficiently, safely, and in an authorized manner)
SUSAR	Serious Unexpected Suspected Adverse Reaction (see definition in chapter 19.4.)
SMF	Study Master File

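### The log transform and percent differences in 18.6.1 are applied to net balance, a signed difference whose smallest important change is given in grams

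*Protocol*

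**What the plan says.** **Transformation.** Section 18.6.1 states: "Data will be log-transformed to improve linearity and model fit and to express outcomes as percent differences". The synopsis gives the same instruction.

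**Outcomes covered.** The next sentence of 18.6.1 reads: "Primary outcomes (PS, PD, and NB) will be referenced to our estimate of the smallest important clinical changes". NB is therefore inside the instruction. Section 18.6.2 carries the method to the secondary outcomes with one exemption: "The statistical analysis on secondary outcomes will be as for the primary, except sensory scale data will not be log-transformed".

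**Definition of NB.** Section 6 has "Net Protein Balance (protein synthesis minus protein degradation" and the synopsis has "whole-body PS, PB, and NB (NB = PS - PB". Both describe a difference of two rates.

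**Threshold and sizing.** Section 18.2 works in grams of protein: an expected difference of 7 g in 165 min, an error of 1.53 g, and "With the smallest important change of 2.2 g protein".

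**Plasma responses.** The synopsis says: "The 4-hour post-prandial response will be calculated as the area under the curve (AUC) using the post-absorptive concentration as the baseline reference". Section 10.3 speaks instead of the total 4-h AUC.

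**Missing values.** Section 18.5.3 foresees no imputation and treats incomplete sequences as missing at random.

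**The concern.** A log scale suits quantities that are always positive and vary by ratios. NB has no floor at zero. The protocol nevertheless fixes the log for it, and gives no offset, alternative scale or rule for values at or below zero. This is not a detail left to an analysis plan: the transformation is stated and its single exception is named.

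Two things are at stake.

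- **Lost or distorted values.** A non-positive NB cannot enter the model. A small positive NB enters as an extreme low value. Each meal has 8 observations, so one lost value is 12.5% of that condition.
- **Interpretation.** The trial is sized on NB in grams and its results are to be judged against a smallest important change. The model as written returns percent differences, and the protocol gives no NB level for converting one to the other.

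NB matters most here: section 16.3 calls net whole-body protein balance the primary outcome measure, and it is the only outcome used for sizing.

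**Working it through.** **1. The plan's own figure is on the gram scale.** Inputs from 18.2: smallest important change 2.2 g, error 1.53 g, 5% type-1 error (taken as two-sided) and 20% type-2 error. Using 1.53 g as a within-subject SD:

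n = [(1.960 + 0.842) × 1.53 × √2 / 2.2]² = 7.59, rounded up to 8.

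This reproduces the stated 8, entirely in grams. A log-scale calculation needs a mean NB or a coefficient of variation, and the protocol has neither. (Section 18.2 calls 1.53 g a standard error. Its use as an SD is a separate matter and does not affect this point.)

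**2. What the log does near zero.** ln(3) = 1.10, ln(0) is minus infinity and ln(−1) does not exist. Going from 0.1 g to 1 g is a step of ln(10) = 2.30, the same as going from 1 g to 10 g. The first step is 0.9 g, below the 2.2 g threshold; the second is 9 g.

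**3. How often NB could be non-positive.** The documents do not say. Assume normal NB on the DIAAS 50% meal (CP3), with p = Φ(−mean/SD) and P(at least one of 8) = 1 − (1 − p)⁸:

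| Assumed mean, g | SD 2 g | SD 3 g | SD 4 g |
|---|---|---|---|
| 2 | 75% | 90% | 95% |
| 3 | 42% | 75% | 87% |
| 5 | 5% | 32% | 59% |

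For example, mean 5 and SD 2 give p = 0.0062 and 1 − 0.9938⁸ = 0.05. With an SD of 1.53 g the chance is 18% at a mean of 3 g and 0.4% at 5 g. At a mean of 7 g and SD of 3 g it is 8%.

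**4. Direction of bias.** Simulation with normal data, equal SDs, a true difference of 7 g between meals and non-positive values dropped. The geometric-mean ratio of what remains is compared with the true ratio of means:

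| Lower-meal mean, SD (g) | Ratio after log | True ratio of means |
|---|---|---|
| 5, 2 | 2.60 | 2.40 |
| 5, 4 | 2.48 | 2.40 |
| 3, 3 | 3.27 | 3.33 |
| 2, 4 | 2.84 | 4.50 |

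Dropping the lowest values raises the lower meal's mean. Small positive values that stay in pull its geometric mean down. Either effect can dominate.

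**5. The threshold as a percentage.** 2.2 g divided by a reference NB:

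| Reference NB, g | 1 | 2 | 4 | 7 | 10 | 20 |
|---|---|---|---|---|---|---|
| 2.2 g as % | 220 | 110 | 55 | 31 | 22 | 11 |

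The 30% in 18.2 does not supply the missing reference. It is a share of the expected difference (2.2/7 = 31%), not a ratio of NB levels.

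**6. Secondary AUCs.** An AUC taken above the post-absorptive concentration is negative when the analyte averages below its fasting level. Section 18.6.2 sends it to the log scale all the same. A total AUC of a concentration is positive and raises no such problem. The synopsis and 10.3 point to different definitions.

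**The case against.** The strongest reply is that the analysed NB is post-prandial, after a meal of about 22 g protein and 810 kcal, and may be comfortably positive in everyone. That could be so, and nothing in the documents excludes it. Several stronger readings are therefore not supported:

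- **That NB is known to be negative when fasted.** The protocol does not say so, and fasted NB is not the analysed value.
- **That the model cannot be fitted.** This holds only if someone's NB is at or below zero.
- **That the contrast is biased toward no difference.** Step 4 shows that the direction turns on unknown inputs.
- **That breakdown is also affected, because it falls after a meal.** The baseline-reference sentence in the synopsis concerns plasma concentrations. Synthesis and breakdown come from the isotope dilution equations; as total rates they are positive and can be logged.
- **That a percent effect can never be judged against 2.2 g.** It can be converted at a stated positive reference NB, and 18.6.1 also reports least-squares means. The protocol simply fixes no reference level.

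It is also true that NB = PS − PB does not carry over to log-scale effects, but since each outcome can be modelled separately this is not an error.

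What survives the reply is the prescription itself: a log for a signed outcome, no rule for values it cannot take, and a threshold on another scale.

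**Conclusion.** The analysis rule is wrong as written for NB and should be changed before the data are analysed. That conclusion needs no assumption: it follows from the definition of NB, the transformation in 18.6.1 and the single exemption in 18.6.2. The mismatch with the gram-scale threshold holds even if every NB is positive.

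The practical size is uncertain. The 5% to 95% range rests on assumed CP3 means of 2 to 5 g, SDs of 2 to 4 g and normality; higher means or smaller SDs make the problem rare. If values are lost, the loss depends on the outcome and the missing-at-random assumption of 18.5.3 does not cover it, but the documents do not show which way the estimate would move.

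For the secondary plasma AUCs the problem is conditional: it arises if they are computed against the post-absorptive baseline, and not if they are total AUCs.

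**What to change.** 1. In 18.6.1 and the synopsis, analyse NB untransformed, in grams over the 4-h post-prandial period, with mean differences and 95% confidence intervals.
2. Judge NB against a threshold in grams: 2.2 g, as used in 18.2. State the period to which it refers, since 18.2 quotes the 7 g difference over 165 min and the trial measures over 240 min.
3. Keep the log and percent differences only for strictly positive outcomes: total PS, total PB and total AUCs.
4. In 18.6.2, exempt any baseline-referenced (incremental) AUC from the log, alongside the sensory scales.
5. Choose one AUC definition and use it in both the synopsis and 10.3.

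The cost is a few sentences in 18.6.1, 18.6.2, 10.3 and the synopsis. No participants, visits or samples are added. The sizing in 18.2 is already in grams, so its inputs still give 8. Making the change before results are seen also avoids a later choice of offset or exclusion.
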